Unfortunately, there is currently no specific defined treatment to prevent or reverse muscle weakness in mechanically ventilated patients. Some recent work suggests that vigorous physical therapy, involving cycling exercise of ICU patient, may improve outcomes (3). Such treatments are labor intensive, however, and few ICU's currently have the manpower or equipment to provide such treatments. In addition, many MICU patients require significant sedation and are too obtunded to realistically participate in any active exercise training regimen. In the University of Kentucky MICU patients are supposed to receive 3 treatments of passive range of motion by physical therapists a week, but compliance with this regimen is poor and only a small minority of patients receive even this modest level of therapy. This minimal level of physical exercise for bed bound ICU patients is typical for patients across the country, with the result that many patients who walk into hospitals need to leave in wheel chairs. Depending upon their health insurance status, some of these patients receive outpatient rehabilitation, but many receive little or no therapy even after hospital discharge.

Recently, a number of companies have developed electrical stimulation devices that can exercise the quadriceps, the major leg muscle, by stimulating this muscle to rhythmically contract. This newer technology represents an advance over older electrical stimulators which can be extremely painful and produce potentially injurious robot-like muscle contractions. Currently this technique is being used to provide rehabilitation to leg muscles after knee surgery in orthopedic patients. The purpose of the present study is to use one of these newer stimulators, the All-Stim 2, in mechanically ventilated MICU patients to provide a means of safely, nonvolitionally exercising the leg muscles of these patients. We postulate that this form of treatment will increase leg muscle strength in these patients, reduce the duration of hospitalization, improve long term mobility, and reduce indices of long term disability.

**Objectives:** List your research objectives. You may reference grant application/sponsor's relevant protocol pages and attach as an appendix in the E-IRB "Additional Information" section, however, a summary paragraph must be provided in the text box below.

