*Research Repositories:* If the purpose of this submission is to establish a Research Repository (bank, registry) indicate whether the material you plan to collect would or would not be available from a commercial supplier, clinical lab, or established IRB approved research repository. Provide scientific justification for establishment of an additional repository collecting duplicate material. Describe the repository design and operating procedures. For relevant information to include, see the UK Research Biospecimen Bank Guidance [\[PDF\]](#) or the UK Research Registry Guidance [\[PDF\]](#)

The basic study design is to:

- (a) obtain informed consent;
- (b) measure magnetic stimulated quadriceps twitch (QuadTw) strength bilaterally;
- (c) randomize patients to treatment with either:

Sham therapy, consisting of bilateral placement of All-Stim 2 electrodes for 30 minutes a day without activation of the electrical circuitry of the unit, or

Active therapy, using the All-Stim 2 electrodes to actively produce a rhythmic quadriceps contraction for 30 minutes a day.

We plan to have a total of 24 patients in the study, with two patients randomized to active treatment for every one patient given sham treatment. As a result we anticipate the final group studied will include 14-16 active treatment patients and 6-8 sham treatment patients.

- (d) continue these regimens daily for 7 days;
- (e) remeasure magnetic stimulated QuadTw on day 8;
- (f) the research team will visit the patient until discharge and will record duration of mechanical ventilation, duration of ICU stay, and total duration of hospitalization; and,
- (g) patients will be visited by a member of the research team at 28 days after study entry to assess the distance that can be walked in 6 minutes (i.e. the 6 minute walk test) and to assess patient well being using the St. Georges Research Questionnaire (SGRQ, a commonly used and extensively validated instrument to assess patient well being).

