#### *Research Repositories*

If the purpose of this submission is to establish a research repository describe the informed consent process. For guidance regarding consent issues, process approaches, and sample language see the Sample Repository/Registry/Bank Consent Template [\[PDF\]](#)

After reviewing the study with the patient and their family, the PI and/or [name] will ask the patient and the family if they wish to participate. The consent form will be reviewed with the patient and their family detailing the risks associated with the planned measurements. If the patient and family agree, the consent form will be signed. If the patient and their family wish they can think about the study and the PI will return the next day. After the consent form is signed, QuadTw measurements will be performed the same day and All-Stim 2 therapy will be started. The PI ([name]) or [name] will obtain all informed consents for the study. To eliminate coercion, all families and study recipients will be told that refusal to participate will in no way influence their care while at the University of Kentucky. Consent will be documented by having both the patient and the next of kin sign the consent form. Because most ICU patients receive some form of sedation, it is the intent of the PI to always inform the family as well as the patient and always have the family member with decision making power over the patient's care (e.g. their spouse or family member with power of attorney) sign the consent form. We will always seek to have the patients also sign the consent form. Under certain circumstances the patient may be so disabled that signage of the consent form is not possible (e.g. the patient is sedated or both hands are instrumented with IV's and pressure transducers). In the event of mental or physical inability of the patient to sign the consent form, the next of kin alone will sign the form.

[Back to Top](#)

**Research Procedures:** Describe the research procedures that will be followed. Identify all procedures that will be carried out with each group of subjects. Differentiate between procedures that involve standard/routine clinical care and those that will be performed specifically for this research project.

It will first be verified that the patient does not meet any exclusion criteria and that informed consent has been obtained.

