**Hospital Outcomes:** After recruitment into studies, electronic hospital records will be reviewed twice a week to determine the time from the point of initial study measurements to successful weaning from mechanical ventilation (defined as remaining off all mechanical ventilation for more than 4 days). Alternative outcomes that will be recorded, for patients that are not weaned from mechanical ventilation, include transfer to a chronic facility for long term weaning from mechanical ventilation (i.e. an LTAC) or death. Deaths will be further subclassified as death due to withdrawal of care and death due to progression of disease. We will also record total ICU stay, total days of hospital stay, and incidence of recurrent respiratory failure, defined as a requirement for reintubation either during the initial hospitalization or at any time out to day 28 after entry into the study. We will also record hospital readmission rates.

**Follow-up Visit (28 days).** At follow-up visits we will assess the distance walked in 6 minutes and we will ask patients if they have returned to work (either full time or part time). We will also have patients fill out the St. Georges respiratory questionnaire (SGRQ) on return visits. This questionnaire evaluates patient's perceptions about their respiratory health, including their assessment of the ability to perform simple tasks of daily living. The PI and/or [name] will visit the patient's domicile (or other site of habitation) to obtain these assessments.

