The PI has studied various aspects of respiratory muscle function and dysfunction over a 25 year period. During this time, the PI has published approximately 100 peer reviewed papers on original research related to respiratory muscle and other critical care topics, as well as 150 abstract presentations at national meetings.

The PI is currently funded by an NIH grant as PI and also receives support as a co-investigator from another NIH grant held by [name]. The PI's laboratory is equipped with a cart containing all the apparatus required to obtain QuadTw measurements. Specifically, the cart is equipped with two MagStim 200 magnetic stimulators equipped with dual figure of eight coils for nerve stimulation, the quad board used for positioning the leg, and a force transducer with a computer interface. This cart is mobile and can be moved to the ICU rooms when needed to assess leg strength. The cart is equipped with sterile wipes that will be used to disinfect all exposed surfaces before and after entrance and exit from patient rooms. Both the Magstim and All Stim 2 units are FDA approved and are in common usage in the USA and other countries for assessment of neurological function and quadriceps conditioning, respectively.

**Potential Risks:** Describe any potential risks or likely adverse effects of the drugs, biologics, devices or procedures subjects may encounter while in the study. Please describe any physical, psychological, social, legal or other risks and assess their likelihood and seriousness.

Use of magnetic twitch stimulation for femoral nerve stimulation is essentially painless. Use of the All-Stim 2 device produces a mild tingling sensation but is also essentially painless at the settings we will use. Removal of the All-Stim 2 electrodes, which have sticky adhesives on their inner surface, could theoretically cause pain in a very hairy individual (this will be dealt with as described below). Both devices could theoretically produce problems in individuals with pacemakers or implanted defibrillators, so patients with these devices will be excluded from the study. We will ask patients to perform a six minute walk test at 28 days after discharge and use a pedometer to assess distance walked. This test has been previously used to assess patient outcomes after ICU discharge (see references 1, 2) with no reported complications. There is essentially no risk to performance of chart reviews or evaluation using the SGRQ.

[Back to Top](#)

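### The 6-minute walk is timed at 28 days after study entry in Study Design item (g), but at 28 days after discharge in Potential Risks

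*Combined protocol and SAP*

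**What the plan says.** All statements are in the current text of the combined protocol and SAP.

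- **Study Design, item (g):** "patients will be visited by a member of the research team at 28 days after study entry to assess the distance" covered in a 6-minute walk. The St. George's questionnaire (SGRQ) is given at the same visit.
- **Potential Risks:** "We will ask patients to perform a six minute walk test at 28 days after discharge and use a pedometer to assess distance walked".
- **Research Procedures, Follow-up Visit (28 days):** the heading gives the day count but not the day from which it runs. The paragraph under it reads "At follow-up visits we will assess the distance walked in 6 minutes and we will ask patients if they have returned to work". The SGRQ is also completed here. The team is to visit the patient's "domicile (or other site of habitation) to obtain these assessments".
- **Research Procedures, Hospital Outcomes:** recurrent respiratory failure is counted during the initial hospitalisation "or at any time out to day 28 after entry into the study".
- **Statistical Analysis Plan:** mentions neither the walk nor the 28-day visit.

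No section describes two separate walk tests, and the document records no protocol changes that would make either statement superseded.

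**The concern.** The same test with the same day count has two different starting points. The terms are not used as synonyms: in Study Design, item (f) follows patients until discharge, and item (g) then counts from study entry.

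The choice of origin affects the comparison of the arms. Long-term mobility is a stated objective, and the walk is the only objective measure of it at follow-up. Entry is fixed before treatment can act. Discharge comes after randomisation, and the Background postulates that treatment will "reduce the duration of hospitalization, improve long term mobility" and lessen disability. If treatment does bring discharge forward, a discharge anchor has active patients walk sooner after randomisation than sham patients, so the contrast in walk distance mixes the treatment effect with a difference in recovery time. If treatment leaves time to discharge unchanged, the discharge anchor only widens the spread of test days.

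The SGRQ and the return-to-work question are affected only insofar as they share the visit; Potential Risks gives a discharge-based time for the walk alone. The day-8 quadriceps twitch (QuadTw) measurement is not affected.

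**Working it through.** **Inputs**

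- Visit time, entry rule: 28 days after entry (Study Design, item (g)).
- Visit time, discharge rule: 28 days after discharge (Potential Risks).
- Baseline: after consent, "QuadTw measurements will be performed the same day and All-Stim 2 therapy will be started" (Informed Consent Process).
- End of treatment: seven daily sessions, then "remeasure magnetic stimulated QuadTw on day 8" (Study Design, items (d) and (e)).
- L = days from entry to discharge. The documents do not give it.

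**Step 1: gap between the rules for one patient**

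- Entry rule: 28 days after entry.
- Discharge rule: L + 28 days after entry.
- Gap = (L + 28) − 28 = L.

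**Step 2: a floor for L from the schedule**

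Count entry as day 1, with sessions on days 1 to 7. The repeat QuadTw on day 8 is then 8 − 1 = 7 days after entry. If entry is counted as day 0 the interval is 8 days, and if therapy starts later than the day of consent it is longer, so 7 is the lowest value. Assume the patient has this test before discharge; the Resources section describes the measurement cart being moved to ICU rooms. Then:

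- L ≥ 7
- discharge-rule visit ≥ 7 + 28 = 35 days after entry
- gap ≥ 7 days, and 7/28 = 25%

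For such a patient the two rules cannot give the same date.

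**Step 3: range over assumed values of L**

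| L assumed (days) | Entry rule | Discharge rule (L + 28) | Gap |
|---|---|---|---|
| 7 | 28 | 35 | 7 |
| 14 | 28 | 42 | 14 |
| 21 | 28 | 49 | 21 |
| 30 | 28 | 58 | 30 |

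Only the first row is tied to the schedule. The others are illustrations.

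**Step 4: difference between arms in mean test day**

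Take mean L over the patients who are discharged and walked, and assume each visit falls on its target day.

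- Entry rule: 28 − 28 = 0.
- Discharge rule: (mean L active + 28) − (mean L sham + 28) = mean L active − mean L sham.

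The second line is zero if treatment does not change L, and negative if it shortens L as postulated.

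**Step 5: does other text settle the origin?**

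- For entry: item (g) is the design statement, and the reintubation window, in the paragraph just before the Follow-up Visit heading, also counts day 28 from entry.
- For discharge: Potential Risks says so outright, and the place of assessment in the Follow-up Visit paragraph fits a patient who has left hospital and does not name the hospital.

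The balance favours entry, but nothing states it. If discharge is meant, it is also unclear which discharge: the sentence after the timing in Potential Risks speaks of leaving the ICU, and Hospital Outcomes provides for transfer to a long-term weaning facility.

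**The case against.** The strongest reply is that this is one stray phrase. Potential Risks mentions the walk in order to say it is safe, not to set a schedule. The design statement says entry, the neighbouring day-28 window says entry, and a home visit is compatible with entry for anyone discharged before day 28. Much of this stands: entry is the more natural reading, and the phrase may well be a drafting slip. It does not remove the defect. The sentence states in plain terms when patients will walk, the procedures paragraph that staff would follow gives no origin, and the form itself says the IRB relies on the Research Description as the protocol summary.

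Other points are fair limits on the claim. The 25% is calendar time, not an effect on walk distance, and it rests on the assumption about the day-8 test. The between-arm formula concerns entry-to-discharge time among patients who are walked, which is not the same as mean total hospital stay, since patients who die contribute no walk. A difference of exactly zero under the entry rule needs visits on the target day, and no visit window is given. The timing of the SGRQ and the return-to-work question is an inference from the shared visit. The consent form and Form B are attachments not seen here, and either may state the origin.

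It can also be said that strength is the outcome for which the SAP gives a before-and-after test, and that with 6–8 sham patients planned, follow-up outcomes are unlikely to be decisive. That limits the weight of the point but is no reason to leave two rules for a stated objective.

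**Conclusion.** The contradiction is real and should be fixed. The two rules differ by L days, at least 7 (25% of 28) for any patient who has the day-8 test before discharge. No effect in metres can be given, because the documents report no lengths of stay. The possible bias is conditional: under the discharge rule the arms differ in mean test day by the difference in mean entry-to-discharge time among those walked, which is zero if treatment does not alter that time. Nothing shows that any patient has been tested under the discharge rule.

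**What to change.** Reconcile the text to one origin. Study entry is preferable, because it is the anchor in the design statement and cannot be moved by treatment.

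- In Potential Risks, time the walk at 28 days after study entry.
- Add the same origin to the Follow-up Visit heading and, in one line, to the Statistical Analysis Plan, which must then name the walk as an outcome.
- State in the Follow-up Visit paragraph that patients still in hospital or another facility on day 28 are assessed there. Item (g) already implies this, but the present description of the visit location does not clearly cover it.
- For patients already enrolled, report the actual study day of each walk and flag any timed from discharge.
- Check the attached consent form and Form B for the same wording.

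If discharge is kept instead, item (g) must change and the plan must say whether ICU or hospital discharge is meant and how transfers count.

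**Cost:** a few wording changes with prior IRB approval, and a walk-date look-up for up to 15 enrolled patients. No new type of measurement is needed. The downside of the entry anchor is that some visits will take place in hospital and some of those patients may be unable to walk on day 28.

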## 12. Progress of the Research

**To meet federal requirements the IRB is relying on your RESEARCH DESCRIPTION as a protocol summary and their expectation is that it is up-to-date.** If the currently approved protocol (or research description) in your E-IRB application is outdated, please make applicable changes, and describe in the field below any substantive changes and explain why they are essential. If none, insert "N/A" in the text field below. If you are closing your study, you may use the space below to summarize the final status of the research.

We have stopped recruitment because of COVID-19 and are waiting for this pandemic to subside before recruiting additional patients.

Note: No changes in the research procedures should have occurred without previous IRB review. Approval from the IRB must be obtained before implementing any changes.

Provide a brief **summary** of any **modifications that affect subject safety and/or welfare** approved by the IRB since the last initial or continuation review (If none, insert "N/A" in the text field below.):

No new modifications.

Attach one copy of the most recent progress report sent to the FDA, if available. All PI-sponsored IND/IDE studies are required to submit a copy of the FDA progress report.

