Inclusion into the study will be considered for all adult patients requiring mechanical ventilation for more than 48 hours for respiratory failure in one of the University of Kentucky adult ICU's. We will include patients regardless of gender, race, or adult age. It is hoped that sufficient minorities and women will be studied so that the subject population is representative of the general patient population, but we will be somewhat constrained by the numbers of available patients and the day to day makeup of the patient population in the UK ICU's. Inclusion of minorities and women will make the study results more generally applicable.

Patients will be excluded:

- (a) if the physician caring for the patient determines that the patient is too unstable to tolerate these measurements,
- (b) if the patient requires high dose pressors (more than 15 mcg/min of norepinephrine or more than 15 mg/kg/min of dopamine),
- (c) if the patient requires more than 80% FiO2 or more than 15 cm H2O of PEEP,
- (d) if the patient has a cardiac pacemaker or implanted defibrillator,
- (e) if the patient has received neuromuscular blocking agents within the 48 hours preceding testing,
- (f) if the patient has a history of a preexisting neuromuscular disease,
- (h) if the patient has profound and uncorrectable hypokalemia (less than 2.5) or hypophosphatemia (less than 1.0)
- (i) if the patient is a pregnant female,
- (j) if the patient is a prisoner,
- (k) if the patient is institutionalized,
- (l) if it is thought that the patient is terminal and will have care withdrawn within 7 days.

Our goal is to recruit 24 total patients into the study. We plan to study an additional 12 patients over the next 12 month period (1 patient/month).

Attachments

**Subject Recruitment Methods & Privacy:** Using active voice, describe plans for the identification and recruitment of subjects, including how the population will be identified, and how initial contact will be made with potential subjects by those having legitimate access to the subjects' identity and the subjects' information.

Describe the setting in which an individual will be interacting with an investigator or how and where members of the research team will meet potential participants. If applicable, describe proposed outreach programs for recruiting women, minorities, or disparate populations as participants in clinical research. Describe steps taken to minimize undue influence in recruiting potential participants.

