Please note: Based upon both legal and ethical concerns, the UK IRB does not approve finder's fees or "cold call" procedures made by research staff unknown to the potential participant. The ORI/IRB does not control permission to any UK listserv, mass mailing list, etc. Investigators must secure prior approval for access and use from owners/managers.

For additional details, see topic "Recruitment of Subjects/Advertising" on ORI's [IRB Survival Handbook web page](#) and the PI Guide to Identification and Recruitment of Human Subjects for Research [\[PDF\]](#).

The PI and/or [name] will meet 3-5 times a week with the MICU attendings at the University of Kentucky to identify patients who would be suitable candidates for this study based on the study inclusion and exclusion criteria. The MICU attending will then approach the patient and the patient's family to determine if the patient agrees to allow the PI and/or [name] to discuss the study with them. The PI and/or [name] will then approach the family and review the study with them.

[Back to Top](#)

**Advertising:** Specify if any advertising will be performed. If yes, please see "[IRB Application Instructions - Advertisements](#)" for instructions on attaching copies of the information to be used in flyers or advertisements. Advertisements must be reviewed and approved by the IRB prior to use. For additional details, see topic "Recruitment of Subjects/Advertising" on ORI's [IRB Survival Handbook](#) web page for the *PI Guide to Identification and Recruitment of Human Subjects for Research* [D7.0000] document [\[PDF\]](#). If you will be recruiting subjects via advertising at non-UK owned or operated sites, you should include a copy of written permission from that site to place the advertisement in their facilities.

Note: Print and media advertisements that will be presented to the public also require review by UK Public Relations (PR) to ensure compliance with UK graphic standards, and equal opportunity language. See [Advertising Instructions](#) for PR contacts. 

No advertising will be performed.

Attachments

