**Safety Precautions:** Describe the procedures for protecting against or minimizing any potential risks, *including risks of breach of confidentiality or invasion of privacy*. Where appropriate, discuss provisions for ensuring necessary medical or professional intervention in the event of adverse events, or unanticipated problems involving subjects. Also, where appropriate, describe the provisions for monitoring the data collected to ensure the safety of subjects. If vulnerable populations other than adults with impaired consent capacity are to be recruited, describe additional safeguards for protecting the subjects' rights and welfare.

Extremely unstable patients, i.e. patients requiring high levels of PEEP, high levels of oxygen or in severe shock, will be excluded from study.

There are no reported adverse effects using magnetic stimulation to assess peripheral nerves except for an isolated report of interference with pacemaker function in one patient. For this reason, we will exclude patients with pacemakers from this study.

There is no risk to the patient for chart review assessment.

There have no reports of previous injury with use of the All Stim 2 device. Application of the All Stim 2 device will require placement of sticky pads on the anterior thighs so, as a result, removal of the device could cause some pain if the sticky pads pull on the thighs of an excessively hairy individual. For this reason, if a patient has significant thigh hair we will warn them of this risk and offer to remove the thigh hair (i.e. by shaving or use of Nair) prior to use of the device. Both the PI and [name] have used the device without incident; we would not expect the average patient to be so hairy that this should represent a serious concern.

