**Benefit vs. Risk:** Describe potential benefits to the subject(s); include potential benefits to society and/or general knowledge to be gained. Describe why the risks to subjects are reasonable in relation to the anticipated benefit(s) to subjects and in relation to the importance of the knowledge that may reasonably be expected to result. If you are using vulnerable subjects (e.g., impaired consent capacity, pregnant women, etc...), justify their inclusion by describing the potential benefits of the research in comparison to the subjects' vulnerability and the risks to them. For information about inclusion of certain vulnerable populations, see the IRB/ORI Standard Operating Procedure for Protection of Vulnerable Subjects [C3.0100] [\[PDF\]](#).

The sensation associated with magnetic stimulation is not painful but is associated with a sudden involuntary contraction of the muscles being stimulated distal to the nerve. The use of the All Stim 2 device produces a tingling sensation.

We do not believe these techniques pose a significant risk to patients, in that no long term adverse consequences should occur providing the exclusion criteria used for this study are rigorously followed.

There are, however, important potential benefits for the patients taking part in this study. Use of this rehabilitation technique may well increase leg strength, improve ambulation, facilitate early mobilization, shorten ICU and hospital stays, improve long term mobility, and increase the long term ability of patients to perform activities of daily living.

**Available Alternative Treatment(s):** Describe alternative treatments and procedures that might be advantageous to the subjects, should they choose not to participate in the study. This should include a discussion of the current standard of care treatment(s).

Currently these patients receive only minimal levels of passive range of motion in the ICU to try to maintain leg muscle function. There

is no alternative exercise regimen that is currently being employed routinely in the MICU at the University of Kentucky.

[Back to Top](#)

**Research Materials, Records and Privacy:** Identify the sources of research material obtained from living human subjects. Indicate what information (specimens, records, data, genetic information, etc.) will be recorded and whether use will be made of existing specimens, records or data. Explain why this information is needed to conduct the study.

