To monitor the long term conduct of the study, including monitoring of adverse effects, we will employ a study monitoring board consisting of [name] and [name]. [name] is a well recognized epidemiologist with a background in statistics and his expertise will be used to make the appropriate statistical analysis of the data obtained from these studies. [name] is the Division Chief of Pulmonary/Critical Care Medicine who has had experience in physician compliance with ICU procedures and monitoring of patient safety in the conduct of invasive ICU procedures and he will have responsibility for assessment of safety issues. This board will review the study at twelve month intervals. At these meetings the board will evaluate the quality of the collected data, completeness of data collected for each patient studied, will review the eligibility form to assess compliance with inclusion/exclusion criteria, reporting of adverse effects by patients or nurses, will determine if the study should be continued or terminated because of safety/risk issues, and, at the final meeting, will review the final results.

Adverse effects will be recorded on study forms and reviewed by the DSMB. The DSMB will consider stopping the study if they conclude that excessive adverse effects clearly linked to one of the treatment arms are occurring. The board will compile a report for each meeting and present their findings to the PI.

To date there have been no adverse events..

No studies have been conducted in the last year so no DSMB assessment of the study has been performed since the last submission of this protocol. We will submit data to the DSMB once new subjects have been recruited.

[Back to Top](#)

**Subject Complaints:** Describe procedures (other than information provided in consent document) for handling subject complaints or requests for information about the research. The procedures should offer a safe, confidential, and reliable channel for current, prospective, or past research subjects (or their designated representative) permitting them to discuss problems, concerns and

questions, or obtain information.

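### Exclusion (b) sets the dopamine limit at 15 mg/kg/min, probably a unit error for mcg/kg/min, so as written the dopamine limit excludes no one

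*Combined protocol and SAP*

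**What the plan says.** The eligibility rules are in the Research Description, under Study Population. Criterion (b) excludes patients on high-dose pressors and puts the qualifying doses in parentheses: "more than 15 mcg/min of norepinephrine or more than 15 mg/kg/min of dopamine". The norepinephrine limit is an absolute rate in micrograms. The dopamine limit is a weight-based rate in milligrams. The dopamine limit appears nowhere else in the documents.

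Other provisions overlap with it:

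- Criterion (a) excludes a patient "if the physician caring for the patient determines that the patient is too unstable to tolerate these measurements".
- Criterion (c) sets numeric ceilings on inspired oxygen and PEEP.
- Safety Precautions states that "patients requiring high levels of PEEP, high levels of oxygen or in severe shock, will be excluded from study", without defining severe shock numerically.

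The written criteria are then put to use in three places:

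- Under Subject Recruitment Methods & Privacy, the study team meets the MICU attendings to "identify patients who would be suitable candidates for this study based on the study inclusion and exclusion criteria".
- Under Data and Safety Monitoring, the board "will review the eligibility form to assess compliance with inclusion/exclusion criteria".
- Under Benefit vs. Risk, the safety claim is conditional: "no long term adverse consequences should occur providing the exclusion criteria used for this study are rigorously followed".

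**The concern.** The purpose of (b) is to give an objective cut-off for haemodynamic instability alongside the clinical judgement in (a). A dopamine limit that no patient could reach does not do that.

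The patient left uncovered is one on high-dose dopamine who is at or below the norepinephrine limit and within the oxygen and PEEP limits. On a literal reading of (b), that patient is kept out only by the treating physician's view under (a) or by the undefined severe-shock wording in Safety Precautions. Someone auditing the eligibility form against the written criterion would pass any dopamine dose.

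The Benefit vs. Risk statement depends on strict application of the exclusions, and strict application of this limit gives no protection. The issue concerns eligibility and safety. It does not bear on the estimand, the sample size or the tests.

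**Working it through.** The limit is stated in the plan, not calculated there, so there is no derived figure to reproduce. The check is a unit conversion.

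**Inputs from the plan (Study Population, criterion (b))**

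- Norepinephrine limit: "more than 15 mcg/min of norepinephrine".
- Dopamine limit: 15 mg/kg/min.

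**Assumption.** Body weights of 50 to 120 kg, for illustration only. The per-kilogram result does not need them.

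**Step 1: the limit as written, per kilogram**

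- 15 mg/kg/min × 60 = 900 mg/kg/hour = 0.9 g/kg/hour.
- 900 mg/kg/hour × 24 = 21,600 mg/kg/day = 21.6 g/kg/day.
- 21.6 g ÷ 1,000 g = 2.16% of body weight per day.

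**Step 2: the same limit at assumed weights, under each unit**

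| Weight (kg) | mg/kg/min: g/hour | mg/kg/min: kg/day | mcg/kg/min: mcg/min | mcg/kg/min: mg/hour |
|---|---|---|---|---|
| 50 | 45 | 1.08 | 750 | 45 |
| 70 | 63 | 1.51 | 1,050 | 63 |
| 100 | 90 | 2.16 | 1,500 | 90 |
| 120 | 108 | 2.59 | 1,800 | 108 |

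For 70 kg as written: 15 × 70 = 1,050 mg/min; × 60 = 63,000 mg/hour = 63 g/hour; × 24 = 1,512 g/day. With mcg: 15 × 70 = 1,050 mcg/min; × 60 = 63,000 mcg/hour = 63 mg/hour.

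**Step 3: can any patient exceed the written limit?** The documents give no dopamine dose range, so take 5 to 100 mcg/kg/min as an assumed span. The written limit is 15,000 mcg/kg/min. The top of the span is 100 ÷ 15,000 = 0.7% of it, so nobody is excluded. With mcg/kg/min, every rate above 15 is excluded. The conclusion does not depend on the assumed span, because the written limit implies more than 1 kg of drug a day at every weight in the table.

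**Step 4: comparison with the norepinephrine limit.** At 70 kg the written dopamine limit is 1,050,000 mcg/min, and 1,050,000 ÷ 15 = 70,000 times the norepinephrine limit. In mcg/kg/min the ratio is 1,050 ÷ 15 = 70.

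**Step 5: where the slip probably arose.** The Research Description page warns that its text boxes reject symbols. Elsewhere in that form a degree sign appears as the letter o (Quadriceps Twitch procedure) and a plus sign stands where plus-minus seems intended (Background). A micro sign turned into m would fit this pattern. A one-character misreading when the PDF was converted to text cannot be excluded. It is less likely, because the form was not meant to accept a micro sign at all and mcg came through intact in the same phrase.

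**The case against.** The best counter-argument concedes the conversion and disputes its importance. The operative words of (b) refer to needing high-dose pressors, and the doses are only in parentheses. A limit of over a kilogram of drug a day is absurd on its face, so an ICU physician would read through it. Candidates are identified with the MICU attendings several times a week, Research Procedures requires the exclusions to be checked before anything is done, and criteria (a), (c) and the severe-shock wording cover most of the risk. No adverse events are reported to date. The intended figure is also unproven: the norepinephrine limit is not weight-based, so it supports mcg but does not by itself establish 15 mcg/kg/min, and the attached Form B, from which this text is said to come, is not available here.

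Much of this stands. The effect is small, the frequency of the uncovered patient is unknown, and the intended value is probable only. Form B is the obvious place to confirm it.

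It does not remove the point. The parenthetical doses are the only objective content of (b), and they are what a compliance review can check. A safety limit that works only because staff silently correct it should be corrected in writing.

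**Conclusion.** The concern holds. The written dopamine limit is physically unreachable, at 21.6 g/kg/day, and the numeric dopamine exclusion is inoperative if applied as written. The probable error is a factor of 1,000 in the unit.

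Confidence is high that the written unit is wrong. That the intended limit is 15 mcg/kg/min is an inference from the neighbouring mcg and the form's handling of symbols.

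The practical loss is one numeric backstop among several safeguards. No calculation in the plan changes, and nothing in the documents suggests that any of the 15 enrolled patients was wrongly included. It should be fixed because the criterion is current, operative safety text and the correction costs almost nothing.

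**What to change.** Before enrolment resumes:

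1. Have the investigator confirm the intended unit, checking the attached Form B.
2. If confirmed, amend the dopamine part of criterion (b) to read: more than 15 mcg/kg/min of dopamine.
3. Check that the eligibility form used for the board's compliance review, which is not in the documents, carries the same unit.
4. Optionally, check the dopamine doses at entry for the 15 patients already enrolled.

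The cost is a one-line IRB modification and a check of one form, plus 15 existing records if the look-back is done. The timing is convenient, since item 12 of the continuation review reports: "We have stopped recruitment because of COVID-19 and are waiting for this pandemic to subside before recruiting additional patients". By the counts in item 5 (Subject Info To-Date), 24 − 15 = 9 patients remain to be enrolled; Study Population speaks of 12 more. On either count, the correction can be in place before the next patient is screened.
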